If moderate symptoms (Grade 2, **APPENDIX 4**) occur, the action should be to have the subject return to the CFRU the next day (day 2) for dosing with the previous days dose or the last tolerated dose, at study physician discretion, under observation. If the dose is tolerated, the subject will continue on that daily home dose for the normal time interval per protocol. If the subject does not tolerate this dose, the subject should receive the last tolerated dose or a 1-2 step dose reduction the next day (day 3) in the CFRU or at home if the planned dose was previously tolerated. If this dose is tolerated, it will be continued as the daily home dose for the normal time interval, then escalation attempted in the CFRU as noted below. If this dose is not tolerated, then the next dose will be a 1-2-step reduction in dosing, and the dose will be given on the CFRU the next day (day 4). If this next dose is not tolerated, then a discussion with the PI will ensue to make a decision about whether to continue the subject on active treatment in the study.

If severe symptoms (Grade 3, **APPENDIX 4**) occur the action should be to treat the subject, and at the study physician's discretion either 1) have them return to the CFRU the next day (day 2) for dosing with a 2-step reduction in dose under observation or 2) discontinue them from the active treatment. If the subject tolerates the dose reduction, then they will remain on that dose for 2 weeks and then return to the CFRU for the dose escalation. A discussion with the PI may ensue to make a decision about whether to continue the subject on active treatment in the study.

If a subject fails dose escalation after three consecutive (with 2-4 weeks between) attempts, he/she will be considered a dose escalation failure and the last tolerated dose will be accepted as the maintenance dose.

For a completed dose escalation with no symptoms, subjects should be observed for 30 minutes. For mild symptoms, subjects should have a 1-2 hours post-protocol observation period. For moderate to severe symptoms, the observation period should be at least 4 hours and up to 24 hours based on symptoms and treatment regimen needed to stabilize the subject.

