7.4. Rescue Medications

Treatment of individual allergic reactions during peanut OIT therapy should be with either an antihistamine and/or epinephrine, along with IV fluids, albuterol and steroids as indicated. Subjects and parents are likely to already have EpiPens[®], but for those who do not, a prescription for EpiPens[®] (or equivalent device) will be provided. Subjects and parents will be trained in proper use and will be able to demonstrate proper technique with the EpiPen[®] (or equivalent device).

Generally, for mild and moderate symptoms, the subject should receive antihistamines, and for more severe symptoms, the subjects should receive epinephrine, antihistamines, and then the other medications as indicated. If severe anaphylaxis occurs at any time, dose escalation will stop and the dose will be reduced to the last tolerated dose and the subject continued on that dose as long-term maintenance without further escalation.

Antihistamines

If a subject requires only antihistamines for treatment of allergic symptoms, the dose escalation can be continued. If symptoms during a build-up day require antihistamines in multiple doses or in combination with other medications (except epinephrine), there should be a dose reduction by 1-2 doses with the next dose given in CFRU. If dose escalation fails or requires treatment after two more escalation attempts each spaced 2 to 4 weeks apart, the dose should be reduced to the last tolerated dose and continued long term without further escalation.

Epinephrine

Any reaction (in CFRU or at home) that requires two or more doses of epinephrine will halt further dose escalation for this individual. Maintenance on the last tolerated dose would be continued.

CFRU

If a single administration of epinephrine is required during in CFRU escalation, the dose should be reduced by two doses, and the subject continued on that dose for four weeks. After 4 weeks at the reduced dose, an escalation attempt may be tried in CFRU.

If a single administration of epinephrine is required a second consecutive time during this escalation attempt, the dose should be reduced by two doses, and the subject continues on that dose for 6-8 weeks. After 6-8 weeks at the reduced dose, an escalation attempt may be tried in CFRU.

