If a single administration of epinephrine is required a third consecutive time during this escalation attempt, the dose should be reduced by two doses and the subject continued on that dose as long-term maintenance without further escalation.

Home

If a single administration of epinephrine use occurs during dosing at home, this epinephrine use is not counted as one of the uses described above, unless severe anaphylaxis occurs at home. The subject should return to CFRU for an observed dose prior to resuming any dosing at home.

8. Study Procedures

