As stated above, an updosing attempt must be made within 3 clinic visits on a given dose, unless updosing is delayed due to administration of epinephrine as defined in Section 7.4 or illness. If the subject fails to successfully increase updosing for three consecutive attempts, updosing will be halted at the last tolerated dose and the subject will continue on that dose as their maintenance dose for the remainder of the study. The subject will be followed for the remainder of the study for safety and immunologic monitoring.

Vigorous exercise is not permitted for at least 2 hours after the dose of oral allergen immunotherapy. Also, there must be at least 1 hour between vigorous exercise and taking a dose of oral allergen immunotherapy. Allergic reactions are still possible when exercise takes place more than 2 hours after the dose.

Should significant systemic symptoms, which may include mild symptoms based on physician discretion or moderate or greater symptoms, be reported during the daily home dosing, the symptom/dosing algorithm will be followed to determine the best course of action. The appropriate treatment will depend on the type and number of symptoms. Subjects will be allowed to take their other daily medications during the build-up and maintenance phases of the study (i.e., antihistamines, albuterol) except where prohibited in this protocol.

Every 13 weeks during the build-up phase, subjects will have blood drawn for mechanistic labs, including basophil activation studies and pregnancy testing, if applicable. Blood will be collected prior to attempted dose escalations, but the decision to updose will be made based on clinical parameters, not the results of the assays.

Weeks 52, 65, 78, and 91– Maintenance Phase

Subjects will undergo updosing until reaching a daily maintenance dose of 4,000 mg and they will remain at that dose and return for follow-up visits at Weeks 52, 65, 78, and 91. Each of these visits will include a physical assessment, spirometry, skin test, and blood draw for mechanistic studies. Based on our previous data using a similar dosing method (Table 2), we expect all subjects on active treatment to reach 4,000 mg between the Week 44 and Week 78 visits.

Week 104 - On Study DBPCFC (to 4,000 mg)

At Week 104 all subjects will have a DBPCFC to 4,000 mg (as per staged challenge above) to assess desensitization. The visit will also include a physical assessment, spirometry, skin prick test and blood draw for mechanistic studies.

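### Sections 6.4 and 7.4 give different dosing instructions after severe anaphylaxis in a subject who stays on treatment

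*Protocol*

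**What the plan says.** Two sections of the protocol direct dosing after a severe reaction during build-up or maintenance.

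- **Section 7.4, general rule.** "If severe anaphylaxis occurs at any time, dose escalation will stop and the dose will be reduced to the last tolerated dose". The sentence goes on to make that dose the long-term maintenance dose, with no later escalation. It applies wherever the reaction happens.
- **Section 6.4, Grade 3 paragraph.** After treating the reaction, the study physician chooses between discontinuation and an observed clinic dose the next day at a two-step reduction. If the reduced dose is tolerated, "they will remain on that dose for 2 weeks and then return to the CFRU for the dose escalation". A discussion with the principal investigator may follow.

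Section 7.4 also has a stepwise rule for a single epinephrine dose during escalation in the clinic (the CFRU). At the first use, "the dose should be reduced by two doses, and the subject continued on that dose for four weeks". Then: "After 4 weeks at the reduced dose, an escalation attempt may be tried in CFRU". The second consecutive use lengthens the wait to 6-8 weeks, and the third ends escalation. The Home paragraph that follows says of a single epinephrine dose at home that "this epinephrine use is not counted as one of the uses described above, unless severe anaphylaxis occurs at home". It also requires an observed clinic dose before home dosing resumes.

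**The concern.** Appendix 4 Grade 3 includes airway angioedema, and wheezing with use of accessory muscles. A severe anaphylactic reaction can therefore meet both triggers. If the subject is not discontinued, staff who open 6.4 find a route back to escalation after 2 weeks, and staff who open 7.4 find that escalation is over. The Home paragraph offers a possible third answer, a re-attempt after 4 weeks, if its exception is taken to move the event onto the clinic steps.

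What is at stake is whether a subject, possibly a child as young as 7, is exposed again to rising allergen doses after a severe reaction. It also matters that like cases are handled alike.

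**Working it through.** The protocol states no figure on this point, so the check is a comparison of rules.

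**Step 1. The rules side by side.**

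| Rule | Trigger | Dose afterwards | Further escalation |
|---|---|---|---|
| 7.4, general | Severe anaphylaxis, any time | Last tolerated dose | None |
| 6.4, Grade 3 | Grade 3 reaction, subject kept on treatment | Two steps down | After 2 weeks |
| 7.4, CFRU, first use | One epinephrine dose during clinic escalation | Two doses down | May be tried after 4 weeks |
| 7.4, two or more doses | Clinic or home | Last tolerated dose | None |

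The first two rows differ on the dose and on whether escalation may resume.

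**Step 2. The dose difference, illustrated from Table 2.** Suppose a subject stable on 479 mg (dose 17) reacts in the clinic to 599 mg (dose 18), and steps are counted from the dose that caused the reaction. Under 7.4 the dose returns to 479 mg and stays there. Under 6.4 it falls to dose 18 - 2 = 16, which is 383 mg, and may rise again after 2 weeks. Section 6.4 is then lower at once by 479 - 383 = 96 mg but permits escalation. Section 7.4 is stricter only on escalation.

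**Step 3. What remains after the other safeguards.**
- Two or more epinephrine doses halt escalation under 7.4, so only single-dose events remain.
- Sections 6.4, 6.5 and 11.2 say that a subject with a severe reaction who receives aggressive therapy should be discontinued, so only events without such therapy remain.
- Hypotension, neurological compromise and mechanical ventilation are listed reasons to discontinue in 6.5 and 11.2, but those lists are permissive.
- Section 12.3.1 defines anaphylaxis in two ways. The first includes hypotension. The second, life-threatening consequences needing urgent intervention, does not require it.

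The residual case is therefore severe anaphylaxis, one epinephrine dose, no aggressive therapy, and no discontinuation.

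**Step 4. Does any text set precedence?** Section 8.3 requires an updosing attempt within three clinic visits "unless updosing is delayed due to administration of epinephrine as defined in Section 7.4 or illness", without saying which 7.4 rule is meant. Section 6.4 refers to the principal investigator those dosing questions that the protocol leaves unanswered; here it gives two answers. Sections 6.5 and 11.2 deal with stopping treatment, not with the dose of someone who continues. None settles the order.

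**Step 5. The Home clause.** It gives no dosing instruction of its own for severe anaphylaxis; it only withdraws an exemption. The clinic steps are tied to escalation in the clinic, and the later ones to repeated use within one attempt ("If a single administration of epinephrine is required a third consecutive time during this escalation attempt"), which a daily home dose is not. The general rule is mandatory and has no limit of place. The better reading is that it governs at home too, but no sentence says so.

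**The case against.** The strongest reply is that 7.4 already decides the matter. Its general rule is mandatory, while the Grade 3 paragraph of 6.4 is worded as what should be done, offers discontinuation as an alternative and allows for a discussion with the principal investigator. Grade 3 is also much broader than anaphylaxis: it includes generalized hives, hard scratching and a freely running nose, so for most Grade 3 reactions the sections do not collide. A life-threatening reaction is a serious adverse event that must reach the NIAID Medical Monitor and the Independent Medical Monitor within 24 hours (12.2.3, 12.5.1). This is a single-centre trial with the investigator available at all times.

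Much of this stands. It makes the case rare and a wrong action less likely. It does not remove the overlap: a severe anaphylactic reaction graded 3 falls under both paragraphs, and 6.4 provides for renewed escalation without excepting it.

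A reader might go further and infer that 7.4 contradicts itself, with a severe home reaction placed on the clinic steps and escalation ending only at a third consecutive use. The documents do not support that. It prefers an implication to an express rule, and it compares a rule for severe anaphylaxis with one for any single epinephrine use. The Home clause is open to misreading, and that is all.

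**Conclusion.** The point holds in narrow form. For severe anaphylaxis in a subject who is not discontinued, 7.4 forbids further escalation and 6.4 allows it after 2 weeks, with no stated precedence. The Home clause adds a possible misreading (a re-attempt after 4 weeks) but is not a separate contradiction.

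The protocol gives no frequency for this case. The expectation in Section 5.2 of severe symptoms in fewer than 1% of subjects covers every kind of severe dosing symptom, so it does not size this subset. The conclusion assumes that severe anaphylaxis, which the protocol does not define separately, is anaphylaxis under 12.3.1. If it means only reactions needing fluid resuscitation or ventilation, the discontinuation provisions would normally apply and the residual case shrinks further.

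A reader might also infer an effect on the primary endpoint or power. Nothing in the documents supports one, and none is claimed. Severity: minor, a patient-safety wording correction.

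**What to change.** Two wording changes in an amendment:

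1. In the Grade 3 paragraph of 6.4, add: *If the reaction is severe anaphylaxis and the subject is not discontinued, the severe-anaphylaxis rule of Section 7.4 applies: no further escalation.*
2. In the Home paragraph of 7.4, replace the exception with: *Severe anaphylaxis at home follows the severe-anaphylaxis rule at the start of Section 7.4, unless the subject is discontinued under Section 6.4, 6.5 or 11.2.*

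While editing, the sponsor should confirm that the last tolerated dose is the intended holding dose, since the two-step reduction in 6.4 can be lower.

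The cost is wording only, with no new dose level, visit or analysis. The downside is that a very few subjects who might have been re-escalated will be capped.

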8.1. Enrollment

The research study will be explained in lay terms to each potential research participant. The potential participant will sign an informed consent form before undergoing any study procedures. Participants will be considered enrolled into the study and assigned a unique study identification number after signing the informed consent/assent document(s).

8.2. Screening/Baseline Visit(s)

The purpose of the screening period is to confirm eligibility to continue in the study. The Screening/Baseline assessments may take place over several visits. All assessments must be completed no more than 10 months (Appendix 1) preceding initiation of peanut/placebo treatment. Baseline/screening visits following requirements below, conducted under a different protocol within the past 10 months prior to IDED, can be used towards this study.

The following procedures, assessments, and laboratory measures will be conducted to determine participant eligibility:

- Consent and assent
- Medical history, including review of all food allergies
- Physical assessment
- Blood draw for peanut-specific IgE and IgG4 measurement
- Skin prick test to peanut extract (neat extract with no dilution, Greer Laboratories, Lenoir, NC)
- Spirometry
- DBPCFC to a 500 mg cumulative total peanut protein
- Pregnancy test, if subject is a female who has undergone menarche and is of childbearing potential (i.e., not otherwise incapable of having children from a previous medical condition, surgery, or other circumstance)

Any of the above items may be repeated within the 10 months preceding initiation of study treatment if warranted, in the opinion of the investigator, by changes in the subject's clinical status.

Double-Blind Placebo-Controlled Food Challenge (DBPCFC) at Screening

Randomization and preparation of the challenge materials will be performed by trained study personnel in the GMP facility at Stanford. Prior to the food challenge, subjects will be asked to restrict the use of oral antihistamines (five half-lives), beta-agonists (12 hours), theophylline (12 hours), and cromolyn (12 hours).

The screening DBPCFC will consist of 7 doses of peanut given every 15-30 minutes in increasing amounts up to a cumulative total of 500 mg of peanut protein. If the study team suspects a reaction may be developing, they may exercise their clinical judgment to separate doses by up to an additional 30 minutes (one hour maximum between doses). The other challenge will consist of placebo material given also in 7 doses. The doses will be 5 mg, 20 mg, 50 mg, 100 mg, 100 mg, 100 mg, and 125 mg. Before each challenge, the subject will have a physical assessment administered by a trained physician's assistant, registered nurse, nurse practitioner, and/or physician of the study team who is blinded to the testing material. The supervising investigator will also be blinded to testing material.

Reactions will be scored using a Food Challenge Symptom Score sheet (see criteria in **Appendix 4**). If the subject begins to have any objective symptoms or subjective symptoms deemed clinically significant, the food challenge will be terminated and the subject will be given appropriate treatment. The subject will be observed for a minimum of two hours after the final administered dose and discharged only when deemed clinically stable by a study physician. All food challenges will be performed under physician supervision. If the subject has no symptoms related to allergic reactions to the peanut ingestion with the DBPCFC, they will not be enrolled in the study.

Separate GI Substudy.

After enrollment into the study, participants who are 18 y.o. or over will be asked, via a separate consent, if they are interested in participating in a study in which biopsies are obtained of the gastrointestinal track to test for safety and efficacy markers. There will be an upper GI endoscopy scheduled at baseline and then again at week 52, 104, and week 117 (or equivalent) of the protocol. We expect to enroll approximately 20 adult subjects in this subset.

Subjects will undergo an endoscopy prior to their IDED. This will be performed by a board certified gastroenterologist at Stanford Endoscopy suite. This will be performed under mild anesthesia using fentanyl, versed and midazolam and

subjects will be observed in the endoscopy recovery room per standard of care. Biopsies will be taken from the esophagus, stomach and duodenum.

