All arms will undergo an Initial Dose Escalation (IDE) Day and updosing regimen with a maintenance phase of OIT or placebo to a maximum of 4,000 mg protein daily, as peanut flour, in the OIT groups, and to a maximum of an equivalent amount of oat flour for the placebo group). (Part III, Figure 1). After maintenance is achieved, all subjects will begin performing DBPCFCs (staged so as to ensure safety) at Week 104 and every 13 weeks thereafter (Part IV, Figure 1). At Week 104, individuals that reach criteria (Part IV, Figure 1) will, based on the randomization that was done at the start of the study, either stop therapy with peanut and be switched to oat flour, or will be maintained on 300 mg peanut protein per day (Parts V, Figure 1). If subjects fail the week 104 DBPCFC they will not be given home doses. Those that fail the week 104 FC will remain in the study and return for a study completion visit at week 117 to meet the primary endpoint (will be analyzed in the intent to treat comparisons). All subjects will be evaluated every 13 weeks thereafter until the end of study.

Individuals in Arm A will be defined as "clinically tolerant" if there is no clinical reactivity at the Week 104 and Week 117 (or equivalent) DBPCFC. Clinical reactivity is defined as any objective reaction based on the Bock's Criteria (**Appendix 4**). Individuals in Arm A who meet the definition of "clinically tolerant" will continue to avoid peanut protein (i.e. continue on 600 mg per day of oat flour) as long as each subsequent DBPCFC (performed every 13 weeks until end of study) shows no clinical reactivity.

Individuals in Arm B will be defined as "desensitized" to a minimum of 300 mg per day of peanut protein if they show no clinical reactivity at DBPCFCs (week 117 (or equivalent) to end of study).

Individuals in Arm C will be defined as "natural loss of responsiveness" if they show no clinical reactivity at DBPCFCs (week 117 (or equivalent) to end of study).

We plan to identify the basic immune mechanisms which can explain the differences in the effects of OIT in individuals who do or do not become clinically tolerant and to determine whether immune monitoring can predict the safety and efficacy outcomes in peanut OIT protocols. After initial screening and enrollment, there are three phases of the study:

- Dose escalation and Build up Phase (Part III, Figure 1)
- Maintenance phase (Part IV, Figure 1)
- Tolerance and Desensitization Testing phase (Part V, Figure 1)

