4.2. Inclusion Criteria

Individuals who meet all of the following criteria are eligible for enrollment as study participants:

- 1. Subject and/or parent guardian must be able to understand and provide informed consent and/or assent as applicable.
- 2. Peanut-allergic subjects between the ages of 7-55 years old.
- 3. Weight equal or greater than 17 kg.
- 4. Sensitivity to peanut allergen as documented by a positive skin prick test result (5 mm or greater diameter wheal relative to negative control) within 6 months preceding enrollment.
- 5. Allergy to peanut based on a double-blind placebo-controlled oral food challenge (DBPCFC) (see **Appendix 4** for scoring details) failed at a cumulative dose ≤500 mg peanut protein within 6 months preceding enrollment.
- 6. All female subjects of child-bearing potential will be required to provide a blood sample for pregnancy testing that must be negative one week before being allowed to participate in the study.
- 7. Subjects must agree to remain in the study area during the trial.
- 8. Subjects must be trained on the proper use of the EpiPen and patient comprehension should be confirmed (see **Appendix 5)** to be allowed to enroll in the study.
- 9. Subjects with other food allergies must agree to eliminate these other food items from their diet so as not to confound the safety and efficacy data from the study.
- 10. Female subjects of child bearing potential must agree to use birth control for the duration of the study.

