The subject's sensitivity to peanut allergen is defined as the dose at which the subject experiences allergic reactions. All symptoms and signs will be evaluated and rated based on a standardized oral food challenge scoring system (Appendix 4).

During the oral food challenge, there should be increased hydration (i.e. about 16 oz or more orally).

Updosing during the DBPCFC will be stopped when the Principal Investigator (or designee) finds symptoms and/or signs that indicate a definite allergic reaction (Bock scoring system (objective, **Appendix 4**) has occurred based on clinically significant changes in reported symptoms, physical findings, or vital signs that the subject is experiencing to the challenge material. The challenge will consist of 7 doses (peanut or placebo), given about every 15-30 minutes for lower doses and about every 45 minutes or longer for higher doses (in bold): 5 mg, 50 mg, 220 mg, **625 mg, 1,000 mg, and 1,050 mg and 1,050 mg** (4,000 mg protein total). The doses for DBPCFCs conducted on or after Week 104 in this
protocol were selected with the rationale that some study subjects will be receiving placebo and would be expected to maintain the same level of sensitivity displayed at the screening DBPCFC to a cumulative dose of 500 mg of peanut protein. Both peanut and oat protein will be concealed in a food that masks the taste. After the last dose of the DBPCFC, the subject will be monitored for 2 hours and then discharged home. Subjects will be considered to have tolerated the OFC if they do not experience any objective reactions by Bock's Criteria (**Appendix 4**).

If the subject experiences reactions, they will be treated with the necessary rescue medications. They will be observed for a minimum two hours after the final administered dose and discharged home only when deemed clinically stable by a study physician.

After the Week 104 DBPCFC, subjects who meet the following criteria will reduce their daily maintenance dose to 300 mg peanut protein daily or to discontinue peanut protein daily dosing entirely (i.e., switch to 600mg oat flour):

- On OIT treatment for minimum 104 weeks,
- Taking daily maintenance dose of 4,000 mg protein for at least 3 months,
- No severe reactions (Bock's Criteria Grade 3, APPENDIX 4) to home dosing from Week 92-Week 104, and/or
- No objective reactions by Bock's Criteria, Appendix 4 at the DBPCFC at Week 104

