13.2. Endpoints

Primary Endpoint

• Proportion of peanut allergic subjects who pass a DBPCFC after the 3 month avoidance period (Week 117 or equivalent) following the end of active treatment phase.

Measurement: A DBPCFC is considered a "pass" if the subject has no clinical reactivity during the challenge (from administration of first dose through observation period lasting 2 hours after administration of the final dose).

Secondary Endpoints:

- Proportion of PA subjects who pass a DBPCFC after a 6 month avoidance period.
- Proportion of PA subjects who pass a DBPCFC after a 9 month avoidance period.
- Proportion of PA subjects who pass a DBPCFC after a 12 month avoidance period.
- Proportion of PA subjects who can successfully complete the build-up phase of peanut OIT to the highest dose (4,000 mg of peanut protein) with only mild (Objective, **APPENDIX 4**) symptoms

- Proportion of PA subjects who can successfully undergo the build-up and maintenance phases of peanut OIT with only mild symptoms.
- Comparison of the proportion of subjects in placebo, avoidance, and 300 mg peanut protein groups who are able to undergo DBPCFCs with no clinical reactivity after initiating OIT.

Measurement of Secondary Endpoints: For measurement of Bullets 1-3 and Bullet 6, see Measurement of Primary Endpoint above. Data for measurement of Bullets 4 and 5 will be collected from subject diaries, reviewed at every updosing visit attempt and DBPCFC visit conducted after successful completion of the Initial Dose Escalation Day.

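### The screening challenge and the endpoint challenge are not tied to one definition of failure, so a subject could enter on subjective symptoms alone and later be scored a pass with no change in allergy

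*Protocol*

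**What the plan says.** **Entry.** Section 8.2 terminates the screening challenge if the subject begins to have "any objective symptoms or subjective symptoms deemed clinically significant". The same paragraph gives one challenge-based bar to enrolment: a subject who "has no symptoms related to allergic reactions to the peanut ingestion with the DBPCFC, they will not be enrolled in the study". Inclusion criterion 5 in section 4.2 asks for a challenge "failed at a cumulative dose ≤500 mg peanut protein within 6 months preceding enrollment" and refers to Appendix 4 for scoring. It does not say whether the failure must be objective.

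**Outcome.** Section 3.1 states: "Clinical reactivity is defined as any objective reaction". Section 8.3 (Week 104) treats a challenge as tolerated "if they do not experience any objective reactions". Section 13.2 scores the primary endpoint as a pass "if the subject has no clinical reactivity during the challenge". Sections 13.1, 13.6 and 13.7 define success as passing at both Week 104 and Week 117; section 13.4.2 names Week 117 only.

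**Doses.** The screening challenge totals 500 mg of peanut protein and the challenges from Week 104 total 4,000 mg.

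**The concern.** Both challenges are scored with Appendix 4, but the line between failing and passing is not drawn at the same place. A subject whose screening challenge was stopped for a reported symptom, with no objective sign, is not clearly excluded. If the same subject shows the same picture at Weeks 104 and 117, the endpoint rule scores a pass. Nothing about the allergy need have changed.

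Three things are at stake:

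- **Arm-specific success rates.** Section 13.4.2 reports these with exact confidence intervals. With 25 subjects in arm C, one extra pass moves the rate by 1/25 = 4 percentage points.
- **Labels.** Section 3.1 calls such a subject clinically tolerant in arm A, or a case of natural loss of responsiveness in arm C. Section 13.4.5 then relates immune features to tolerance, so misclassified passes would blur that work.
- **Power.** Section 13.7 rests on a placebo success rate of 0.05 or less. Unchanged subjects who pass would raise that rate.

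**Working it through.** **Step 1. The passages side by side.**

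| Place | Rule | Objective reaction needed? |
|---|---|---|
| 8.2, stopping the screening challenge | Objective, or clinically significant subjective, symptoms | No |
| 8.2, bar to enrolment | No allergic symptoms at all | No |
| 4.2, criterion 5 | Challenge failed at 500 mg or less | Not stated; refers to Appendix 4 |
| 3.1, 8.3, 13.2, pass from Week 104 | No objective reaction | Yes, to fail |

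The first two rows allow a subjective-only entry, the third does not exclude it, and the fourth would score the same picture as a pass.

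**Step 2. Reproduce the planned power.** Inputs from section 13.7: 60 subjects in arm A, 25 in arm C, success rates pA = 0.35 and pC = 0.05, two-sided alpha 0.05. With the pooled two-proportion formula:

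- p̄ = (60·pA + 25·pC)/85
- SE0 = √[p̄(1 − p̄)(1/60 + 1/25)]
- SE1 = √[pA(1 − pA)/60 + pC(1 − pC)/25]
- power = Φ[(pA − pC − 1.96·SE0)/SE1]

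Here p̄ = 0.2618, SE0 = 0.1046 and SE1 = 0.0754, so power = Φ(1.26) = 89.6%. The protocol states 90%. The same formula reproduces every cell of the section 13.7 table.

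**Step 3. Add subjective-only entrants (assumptions, not in the protocol).** Let a share s of subjects in both arms enter on subjective symptoms alone, and let a fraction f of them pass the later challenges untreated. All others keep the planned rates. In arm A these entrants pass at f or 0.35, whichever is larger.

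- pC = (1 − s)·0.05 + s·f
- pA = (1 − s)·0.35 + s·max(f, 0.35)

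For s = 5%, f = 0.5: pC = 0.0475 + 0.025 = 0.0725 and pA = 0.3325 + 0.025 = 0.3575. Then p̄ = 0.2737, SE0 = 0.1061, SE1 = 0.0807, and power = Φ(0.95) = 83%.

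For s = 10%, f = 0.5: pC = 0.045 + 0.05 = 0.095 and pA = 0.315 + 0.05 = 0.365. Then p̄ = 0.2856, SE0 = 0.1075, SE1 = 0.0855, and power = Φ(0.69) = 76%.

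| s | f | pA | pC | Power |
|---|---|---|---|---|
| 0 | – | 0.350 | 0.050 | 90% |
| 5% | 0.25 | 0.350 | 0.060 | 86% |
| 5% | 0.5 | 0.358 | 0.073 | 83% |
| 10% | 0.25 | 0.350 | 0.070 | 82% |
| 10% | 0.5 | 0.365 | 0.095 | 76% |
| 10% | 1 | 0.415 | 0.145 | 70% |
| 20% | 0.5 | 0.380 | 0.140 | 60% |

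**Step 4. Size of the later test.** The screening doses sum to 5 + 20 + 50 + 100 + 100 + 100 + 125 = 500 mg. The later doses sum to 5 + 50 + 220 + 625 + 1,000 + 1,050 + 1,050 = 4,000 mg, eight times as much. Under sections 13.1 and 13.6 the subject must pass this challenge twice. Both facts push f down, so the rows with high f are the least plausible.

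**The case against.** **Eligibility may already be objective.** The section 8.2 wording is a stopping rule, and the sentence on subjects without symptoms bars some from entry without saying that everyone else qualifies. Eligibility is set by criterion 5, which cites Appendix 4, and that appendix refers to objective criteria in its title. This stands as a possible reading, so it cannot be said that subjective-only entry is the stated rule. But criterion 5 never says so, and section 8.2 names no further test after a challenge stopped for subjective symptoms.

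**Reported symptoms also count later.** Section 8.3 mentions reported symptoms when it describes stopping the later challenges, and section 13.4.2 counts an unevaluable test as a failure. Some subjective-only presentations might therefore fail after all. That narrows the gap, but the pass rule in section 8.3 remains: "Subjects will be considered to have tolerated the OFC if they do not experience any objective reactions".

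**The later test is much harder.** This stands in full, for the dose and for the two-challenge requirement. It limits the effect without excluding it.

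**The planned placebo rate may already include the effect.** It comes from cited literature. If that source used a similar entry rule, part of the inflation is in the 0.05 already. The protocol does not settle this.

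**Tempting stronger readings.** A reader might infer that the primary test is biased. It is not: the same entry rule applies to all arms before randomization, so under the null the comparison of A with C is unaffected. A reader might also add 2.5 to 5 points to the placebo rate alone and hold arm A at 0.35, which gives 80% power at 0.075 (also the protocol's tabulated figure) and 69% at 0.10. That is inconsistent, because arm A would contain such entrants too, and because the addition leaves in the 0.05 that these subjects already contributed.

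**Conclusion.** The point holds as an unreconciled definition. As written, the protocol permits, but does not clearly intend, entry on subjective symptoms and a later pass on the absence of objective ones. The possible consequences are inflated success rates in each arm, weaker tolerance and natural-loss labels, and some loss of power. The type I error of the A versus C test is not affected.

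The size is uncertain. With 5–10% subjective-only entrants, half of whom would pass untreated, the rates become about 0.358 vs 0.073 to 0.365 vs 0.095, and power is about 83% to 76% instead of 90%. Both shares are assumptions, and the true effect is probably smaller for the reasons in step 4. Appendix 4 marks objective items in bold; the bold is not visible in the text available here, so no particular symptom is classified and no share can be estimated from it.

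**What to change.** 1. **Reconcile the passages.** Bring section 4.2 (criterion 5) and section 8.2 into line with sections 3.1, 8.3 and 13.2, so that a failed challenge for eligibility has the same Appendix 4 definition as the endpoint. The rule for stopping a challenge for safety is a separate matter and stays with the investigators.
2. **Pre-specify a sensitivity analysis.** Section 8.2 already has screening reactions scored with Appendix 4. Use those scores to repeat the A versus C comparison and the arm-specific success rates in subjects with an objective screening reaction. This restriction uses a baseline variable, so the arms stay comparable by randomization. It can also leave out subjects whose challenge was stopped before an objective sign appeared, so it supports the intent-to-treat analysis and does not replace it.

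The cost is a few more screen failures if the definition is aligned before enrolment ends, or one extra analysis in a slightly smaller sample if it is not. No new data are needed.
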